| Informed Consent | X | | | | | |
| Inclusion/Exclusion Criteria | X | | | | | |
| Randomization (RCT only) | X | | | | | |
| Demographic & History Form* | X | | | | | |
| Physical Exam | X | | X | X | | |
| Procedure & Perioperative Information | | X | | | | |
| Other Device Documentation | | ◆ | | | | |
| Chart Review* | | | | X | | X |
| Patient Questionnaire #1 (EDC)* | ● | | | | | |
| Patient Questionnaire #2 (EDC)* | | | ● | | | |
| Patient Questionnaire #3 (EDC)* | | | | ● | | |
| EQ-5D-5L (EDC)* | ● | | ● | ● | ● | ● |
| KOOS, JR, HOOS, JR (via mymobility App). Control patients will complete in the EDC* | ● | | ● | ● | ● | ● |
| Adverse Event Form | | ◆ | ◆ | ◆ | ◆ | ◆ |
| Medical Event Log | | ◆ | ◆ | ◆ | ◆ | ◆ |
| Protocol Deviations* | ◆ | ◆ | ◆ | ◆ | ◆ | ◆ |
| Study Completion* | ◆ | ◆ | ◆ | ◆ | ◆ | ◆ |
| Time Documentation (Pilot Only) | X | X | X | X | | |

X Completed by Investigator or Designee

● Completed by subject (required)

◆ Completed by Investigator or Designee as applicable

* Forms that can be directly entered into the EDC system

V. Introduction and Purpose

Postoperative rehabilitation after total joint arthroplasty (TJA) has traditionally been initiated via discharge to a rehabilitation facility or through formal outpatient physical therapy (PT).¹ This has resulted in the cost of approximately \$648 million per year for PT after primary TJA, with up to 25% of these costs utilized on less common modalities.² As elective TJA patients have increased their mobility in the early postoperative period and hospital or ambulatory surgery center (ASC) length of stay has decreased over time, patient-initiated therapy has become an emerging alternative for postoperative recovery. Previous randomized controlled trials have demonstrated that monitored home exercises can have equivalent outcomes when compared to formal outpatient PT after TJA for both range of motion (ROM) and patient reported outcome measures (PROMs).³⁻⁸ However, there remains a substantial subgroup of patients (up to 20%) who may crossover to formal PT following patient-initiated therapy, highlighting a potential opportunity to provide an optimized home program that provides more effective simulated physical therapy in the postoperative TJA period.

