Eligible candidates who express interest in study participation will be offered Informed Consent. All potential study subjects will be required to participate in the Informed Consent process and will not be considered enrolled in the study until the candidate has signed and dated the IRB/EC approved subject Informed Consent Form (ICF). Study data cannot be collected until the candidate has completed the informed consent process and signed and dated the IRB/EC approved ICF.

All study subjects will undergo preoperative and postoperative clinical evaluations as part of the standard of care at each institution. Post-operative clinical evaluations will be conducted after surgery (30 and 90 days). A virtual visit, utilizing the mymobility App or EDC system, will occur at 180 and 365 days post-op.

The target population is patients who have made the decision to undergo a total hip, total knee, or partial knee replacement. The target population is further defined in the inclusion/exclusion criteria in **Section VIII**.

RCT: Primary Endpoint

1. Demonstrate non-inferiority of the study group in the number of readmissions through 30 days post-op.

RCT: Secondary Endpoints

1. Non-inferiority of the mymobility cohort for PROMs (HOOS, JR., KOOS, JR.) and EQ-5D-5L.
2. Manipulation Rates (knee), Timed Up and Go (TUG) and single leg stance test (SLS).
3. Satisfaction/Engagement: Assess differences between the study groups in subject satisfaction from Custom Satisfaction Survey(s).
4. Resource Utilization: Assess differences in resource-utilization in the study group for the entire episode of care (90 days postoperative). Potential data collection points include number of PT visits, discharge disposition, emergency room visits, readmissions, reoperations, unscheduled surgeon visits, and reduction in time processing paperwork and approvals from PT.

VIII. Study Population

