4. EQ-5D-5L
5. KOOS, JR. or HOOS, JR.
6. Patient Questionnaire #1
7. Protocol Deviations (as applicable)
8. Study Completion (as applicable)

Subjects may be consented up to 180 days prior to surgery. Preoperative forms, mymobility App registration, and Apple Watch distribution must be completed during the pre-op interval. The suggested visit window to allow best utilization of pre-operative mymobility App content is 14-30 days prior to the surgery.

Data from Standard of Care (SOC) assessments performed prior to enrollment may be used provided that data was obtained within 180 days of surgery and the patient consented to its use. In the event that surgery is rescheduled to a date greater than 180 days from enrollment, the site should reaffirm study participation with the subject prior to surgery and reobtain study assessments.

Physical exam assessments are intended to be completed at in-person visits. However, remote visits may be utilized to capture assessments if institutional restrictions prevent an in-person visit. Protocol deviations will document incomplete data.

F. Surgical Technique

Standard operative procedures will be followed and all surgical procedures will be performed under aseptic conditions. Investigators will implant all commercially-available partial or total knee components or total hip components in compliance with corresponding labeling requirements and in accordance with appropriate surgical technique(s).

G. Surgical and Discharge (Data Collection)

The following data will be collected about the surgery and immediate post-operative period, up to and including subject discharge:

1. Procedure & Perioperative Information
 - a. Implants and instrumentation data
 - b. Length of Stay and Discharge Disposition
2. Other Device Documentation (as applicable)

3. Adverse Event Form (as applicable)
4. Medical Event Log (as applicable)
5. Protocol Deviations (as applicable)
6. Study Completion (as applicable)

Previously enrolled patients who received a hip resurfacing procedure will be classified as total hip arthroplasty. Additionally, if the actual procedure differs from the procedure selected on the inclusion/exclusion form, then the inclusion/exclusion form should be updated to the actual procedure.

H. Postoperative Follow-up Procedures (Data Collection)

Postoperative clinical evaluations/assessments will be conducted at the following visit intervals:

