For sites participating in both the Pilot and RCT cohorts, enrollment in the RCT cohort will begin once enrollment is complete at the site for the pilot cohort. Randomization will occur during the pre-operative visit after subjects have signed the ICF for participation in the study. A standard, stratified 1:1 randomization of total hips, total knees, and partial knees will be used to assign subjects to either the mymobility/Apple Watch study group or the standard of care control group. Stratification will ensure that within hips and knees, each procedure type will have a balanced allocation of control

and study patients.

a. Study Group (N=500)

Once randomization is completed, all subjects who were randomized to the mymobility group (mymobility/Apple Watch platform) will undergo all routine study procedures outlined in **Section XI**. In addition, each subject will:

- i. At the preoperative, 30 day and 90 day visits, subjects will undergo a physical exam.
- ii. At the 30 day and 90 day visits, subjects will undergo a Timed Up and Go (TUG) assessment and Single Leg Stance (SLS) assessment. A description of each assessment is listed below:
 - a. TUG assessment: the subject will be asked to rise from a sitting position, walk 3 meters as quickly as they feel safe and comfortable, turn around and walk back to take a seat in the chair. They will be timed from initiation of standing to a return to the sitting position. The subject will get one practice trial prior to scoring the assessment.
 - b. SLS assessment: Three, one-minute maximum, timed observations will be obtained. The average of the three timed observations will be calculated at the time of data analysis.

b. Control Group (N=500)

Subjects randomized to the control group will undergo traditional, standard of care procedures at their institution without the use of the mymobility platform

- i. Control subjects will receive the standard of care (SOC) at the institution, including postoperative PT, and go through normal preoperative standard of care including joint camp classes, preoperative medical clearance, and traditional preoperative education.
- ii. Control subjects will not be provided with the Apple Watch or mymobility App.
- iii. Control subjects will go through each institution's standard of care (SOC) perioperative management pathway.

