- iv. Control subjects will complete the same PROM surveys and patient questionnaires as the mymobility group but they will be completed through the EDC system or on paper.
- v. Control subjects will complete all Timed Up and Go, Single Leg Stance and ROM assessments, equivalent to the mymobility group above.

XII. Reporting

A. Activities Required Prior to Initiation of the Study

1. Institutional Review Board/Ethics Committee Informed Consent Approval

A Sponsor-approved Informed Consent Form (ICF) template (Appendix 3) will be provided for IRB or EC submission and approval. If the IRB or EC requires revisions to the provided ICF, the requested revisions must be submitted by the Investigator to the Sponsor for review and approval. Once the Sponsor has reviewed and approved the revision, the ICF will be re-submitted to the IRB or EC for final review and approval. A copy of the final IRB or EC approved ICF must be submitted to the Sponsor.

B. Clinical Data Collection/Submission

The Sponsor will collect all data in a central database (e.g. EDC, mymobility, HealthKit). The Sponsor will manage the collection of data into the Apple Health and Fitness Recorder App. The management of all study data received by the Sponsor will be the responsibility of the Sponsor or its designee. The use or disclosure of all protected health information will comply with all relevant data privacy and data security laws and requirements. All information will be treated with strict adherence to professional standards of confidentiality and will be held by the Sponsor under adequate security and restricted accessibility.

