Subjects using the mymobility application will be evaluated for pain, function, quality of life, and early post-operative outcomes. Data collected in this study will be summarized descriptively and descriptive summaries will be the basis of any study reports issued. These summaries may be used for interim study reports and may also be used to support regulatory submissions, presentations, and/or publications. Additional surgical technique and instrumentation data may be collected and evaluated.

A. General Statistical Methods

Statistical methodology will consist of summarizing collected data descriptively. Categorical data (e.g., gender or race) will be summarized using counts and percentages, and 95% Confidence Interval (CI), over the time periods of interest. Continuous data, such as age, will be summarized by using means, medians, standard deviation, minimum, maximum, and 95% CI over the time periods of interest. Routine summaries of complication data is represented by frequencies and percentages. Subgroup analysis on a variety of data will also be performed. Exploratory data analyses using statistical models to discover relationships between demographics, subject adherence, HealthKit data and outcomes will also be performed.

B. General Assumptions

The primary endpoint will be subjected to a power analysis, allowing for an estimation of the number of RCT subjects needed to demonstrate clinically significant differences between outcome measures. Below is the initial analysis on the primary endpoint.

1. Readmission Rate

A 2015 journal article in PLOS ONE used meta-analyses and the University of Wisconsin demonstrated the overall 30-day readmission rate to be 5.4%.³¹ The 5.4% readmission rate is similar to the readmission rates reported in a 2016 JOA article on readmission rates for hips (% across all orthopedics 5.8%) and a 2017 JBJS article on readmission rates for knees (5.8%).

Based on an assumed readmission rate of 5.4% in both the control and study group and a non-inferiority margin of 4.5%, a total sample size of 794 patients will provide 80% power while controlling the alpha-error at 0.05.

C. Sample Size

1. RCT cohort

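### No between-arm analysis method is stated for the RCT, and no RCT comparison uses the baseline PROM scores and randomisation strata already collected

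*Combined protocol and SAP*

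**What the plan says.** Section XVI.A gives the general method: "Statistical methodology will consist of summarizing collected data descriptively". It covers counts, percentages, means, medians and 95% confidence intervals. The opening of Section XVI adds that "descriptive summaries will be the basis of any study reports issued". The only models mentioned in XVI.A are exploratory: "Exploratory data analyses using statistical models to discover relationships between demographics, subject adherence, HealthKit data and outcomes will also be performed". None of these compares the randomised arms.

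The RCT is set up for more than description. The first secondary endpoint in Section VII is "Non-inferiority of the mymobility cohort for PROMs (HOOS, JR., KOOS, JR.) and EQ-5D-5L". Sections XVI.B and XVI.C give the primary endpoint a 4.5% margin, alpha of 0.05, 80% power and a success rule. That rule refers to the statistical methods described, but no test, interval method, covariate or handling of strata is described.

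The data for adjustment exist. Sections IV and X.E collect EQ-5D-5L and KOOS JR or HOOS JR before surgery. Section XI.B.2 says that "A standard, stratified 1:1 randomization of total hips, total knees, and partial knees will be used to assign subjects".

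Two further provisions bear on this. Section X.G says that "if the actual procedure differs from the procedure selected on the inclusion/exclusion form, then the inclusion/exclusion form should be updated to the actual procedure". Section IV lists "KOOS, JR, HOOS, JR (via mymobility App). Control patients will complete in the EDC", and Section XI.B.2.b says of the control group's surveys that "they will be completed through the EDC system or on paper".

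**The concern.** A non-inferiority claim needs an estimated difference between arms, an interval for it and a margin. For the PROMs the plan gives none of these. For readmission it gives the margin but not the estimator or the interval. Read literally, the descriptive wording in XVI.A conflicts with the testing language in XVI.C.

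If the gap is filled by comparing raw means, the trial gives up precision that it has already paid for. The baseline score usually explains part of the variation in the follow-up score, and a design stratified by procedure is naturally analysed by procedure. The loss matters most for HOOS JR and KOOS JR, because each is completed by only one part of the RCT cohort.

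A stratified analysis also needs the stratum as it stood at randomisation. The operation actually performed is a post-randomisation variable. If the updated inclusion/exclusion form were the source of the analysis stratum, the wrong variable would be used.

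**Working it through.** **The plan's own figure.** Inputs from XVI.B: 5.4% in both arms, margin 4.5 points, 80% power, alpha 0.05. For non-inferiority of two proportions with unpooled variance and one-sided 0.025:

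n per arm = 2 × 0.054 × 0.946 × (1.960 + 0.842)² / 0.045² = 396.002, rounded up to 397, total 794.

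This matches the plan exactly. One-sided 0.05 would give 312 per arm, 624 in total. With 20% loss, 794 / 0.8 = 993, so 1,000 is adequate. The sample size is therefore that of an unadjusted, unstratified comparison judged by a two-sided 95% interval.

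**PROMs: inputs.**
- 500 per arm (XI.B.2) and 20% loss (XVI.C): 400 per arm.
- KOOS JR is for knees only and HOOS JR for hips only (Synopsis, Scores/Performance Assessments).
- Assumed: 35% hips and 65% knees. This gives 0.65 × 400 = 260 knees and 0.35 × 400 = 140 hips per arm. The documents give no split.
- Assumed: baseline-outcome correlation r of 0.3 to 0.5. The documents give none.
- Illustrative margin of 0.20 SD. The documents give no PROM margin.

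**PROMs: formulas.** Compared with follow-up scores alone, ANCOVA multiplies the variance by 1 − r²: 0.91 at r = 0.3 and 0.75 at r = 0.5, a fall of 9 to 25%. In SD units:
- SE = √(2(1 − r²)/n)
- half-width = 1.96 × SE
- power with no true difference = Φ(0.20/SE − 1.96)

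| Instrument | n per arm | Half-width, unadjusted | r = 0.3 | r = 0.5 | Power, unadjusted | r = 0.3 | r = 0.5 |
|---|---|---|---|---|---|---|---|
| EQ-5D-5L | 400 | 0.139 | 0.132 | 0.120 | 81% | 84% | 90% |
| KOOS JR | 260 | 0.172 | 0.164 | 0.149 | 63% | 67% | 75% |
| HOOS JR | 140 | 0.234 | 0.223 | 0.203 | 39% | 42% | 49% |

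For example, KOOS JR at r = 0.5: SE = √(2 × 0.75/260) = 0.0760; half-width = 1.96 × 0.0760 = 0.149; power = Φ(0.20/0.0760 − 1.96) = Φ(0.67) = 75%.

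The relative gain does not depend on the assumed hip share: half-widths shrink by factors of √0.91 = 0.954 and √0.75 = 0.866 whatever the split.

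**Readmission.** Stratifying replaces the total variance p(1 − p) with the weighted within-stratum variance. The shares and rates below are assumed (hip, total knee, partial knee), each set averaging 5.4%. Power is at 400 per arm, against 80.4% unstratified.

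| Shares | Rates | Variance ratio | Power |
|---|---|---|---|
| 0.40 / 0.50 / 0.10 | 5.8 / 5.4 / 3.8% | 0.999 | 80.4% |
| 0.35 / 0.50 / 0.15 | 3.0 / 7.5 / 4.0% | 0.991 | 80.7% |
| 0.35 / 0.50 / 0.15 | 2.0 / 9.0 / 1.33% | 0.975 | 81.4% |

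The gain is about one power point or less even with widely differing stratum rates.

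**The case against.** The strongest reply is that the primary comparison is inferential and success rests on readmission alone, where adjustment adds almost nothing. That stands. A reader might infer from XVI.A that the RCT is to be analysed only descriptively, but XVI.B and XVI.C set a margin, an alpha and a success rule. What is missing is the method.

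A reader might also infer that the plan prescribes unadjusted comparisons. It does not say so. That reading rests on silence, although 794 matches an unadjusted calculation.

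Nor does leaving out the covariates bias the result. Chance imbalance in a randomised comparison is already allowed for in the confidence interval, so the case for adjustment is precision.

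The form rule invites the inference that the stratum is destroyed. The documents do not show this. Section X.G changes the inclusion/exclusion form and does not mention the randomisation record. Section IV lists randomisation as its own item, X.E says it is recorded in EDC, and XII.B says that audit trails exist. What remains is a risk: X.E places randomisation under the inclusion/exclusion item, and recovering a design variable from an audit trail is a poor substitute for a protected field.

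The survey-mode difference is real. KOOS JR is an example task on the app's list and the watch reminds patients of listed tasks (IX.B.1 and IX.B.4), while controls use EDC or paper. A reader might conclude that follow-up should move to EDC in both arms. That would create a change of mode between baseline and follow-up in the study arm only, and controls could still answer on paper. The documents do not show that this would be better.

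**Conclusion.** The point holds as a gap in specification with a quantifiable cost in efficiency. No stated RCT comparison has a between-arm method, and the baseline scores and procedure strata already held go unused.

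The gain is moderate for the PROMs and negligible for readmission. The PROM figures rest on the assumed correlation, the assumed hip share, 20% loss and an illustrative margin. They also take comparison of follow-up scores as the alternative, since the plan does not say which comparison it intends. Figures based on 400 per arm apply to EQ-5D-5L only.

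The primary sample size and success rule are unaffected. Even with adjustment, HOOS JR stays below 50% power at 0.20 SD under these assumptions, so adjustment alone does not make that comparison well powered. No PROM non-inferiority conclusion is possible until margins are stated.

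**What to change.** In XVI.A, replace the descriptive-only wording for the RCT cohort with:

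- **PROMs.** ANCOVA or a mixed model, run separately for EQ-5D-5L (all subjects), KOOS JR (knees) and HOOS JR (hips), adjusting for baseline score and procedure as randomised. For HOOS JR the procedure term drops out, because hips form a single stratum. State the PROM non-inferiority margins before any comparative analysis.
- **Readmission.** A risk difference stratified by procedure as randomised (Mantel-Haenszel or Miettinen-Nurminen), with a two-sided 95% confidence interval compared with the 4.5-point margin.
- **Stratum.** Keep the as-randomised procedure in a separate locked field, so that the form update in X.G cannot change the stratum used in analysis. The X.G instruction itself can stay.
- **Survey mode.** Report the difference between arms in KOOS/HOOS JR mode and prompting as a limitation of the PROM comparison.

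The cost is analysis code, one database field and a clinical judgement on the PROM margins. No further patients, visits or questionnaires are needed.

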Potential subjects will be screened from each investigator's subject population. Subjects may be pre-screened for eligibility based on the inclusion and exclusion criteria. The site will maintain a Screening Log to track all screened subjects, including subjects who do not meet the study criteria and those who decline to participate. The log will document general demographic information for each screened patient as well as reasoning for patients who do not enroll.

B. Offer Study Participation

Study participation will be offered to each eligible patient presenting as a potential candidate. Eligible candidates who express interest in study participation will be offered Informed

Consent. Prior to patient involvement in the study, the patient must participate in the Informed Consent process and sign and date the IRB/EC-approved ICF.

C. Informed Consent Process

For candidates that express interest, the Investigator or Designee will describe relevant study information, including the purpose, procedures, alternative treatments, possible risks, and potential benefits associated with study participation. The Investigator or Designee will also describe the types of patient information that may be collected or analyzed during the study and with whom that information may be shared. The Investigator or Designee will also review, along with the candidates, the ICF approved by both the governing IRB/EC and the study Sponsor. Candidates shall have sufficient time to read and understand the IRB/EC approved ICF and discuss whether they wish to participate in the study. Candidates will be asked to acknowledge whether all of their questions and concerns have been addressed to their satisfaction. Any questions that candidates may have will be addressed appropriately by the Investigator or Designee. Candidates will be further instructed that they are free to obtain additional information from the Investigator or Designee at any time, that they are free to decline participation, and that they are free to withdraw their consent and authorization and discontinue their participation at any time without prejudice but for the requirement to return the watch if they withdraw prior to completing the final follow-up visit.

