2. EQ-5D-5L
3. KOOS, JR. or HOOS, JR.
4. Patient Questionnaire #2 (at 30 day visit)
5. Patient Questionnaire #3 (at 90 day visit)
6. Chart Review (at 90 and 365 day visits)
 - a. Complications, readmissions, ER visits, non-SOC visits, physical therapy
7. Medical Event Log (as applicable)
8. Adverse Event Form (as applicable)
9. Protocol Deviation (as applicable)

10. Study Completion (as applicable)

Sites will be required to follow subjects postoperatively for 365 days +/- 60 days. Unless the study is otherwise closed, data will continue to be collected until the subject completes the study per the protocol, voluntarily withdraws from the study, is withdrawn from the study by the investigator, is lost to follow-up, undergoes revision to remove the implanted device, or expires. See Management of Incurrent Events (**Section XII**) for additional details. Reason(s) for study completion must be documented on the **Study Completion Form**.

Post-op physical exam assessments are intended to be completed at in-person visits. However, remote visits may be utilized to capture assessments if institutional restrictions prevent an in-person visit. Protocol deviations will document incomplete data.

XI. Pathway Specific Procedures

A. mymobility Procedures – Correlative Analytics Cohort (N=10,000)

These study procedures apply to all study subjects in all cohorts who have signed the ICF and are selected to receive the mymobility platform. The correlative analytics cohort includes all subjects in all three cohorts of the study who receive the mymobility platform. Procedures for control subjects in the RCT cohort are discussed in **Section XI**.

1. Preoperative Visit (up to 180 days before surgery)

- i. If not previously completed, the subject will go through the full informed consent process and will sign and date the EC/IRB-approved ICF as outlined in **Section X**.
- ii. Subject registration for the mymobility App includes the creation of a study Subject ID number via the study EDC system and placement into the master Zimmer Biomet electronic data collection (EDC) database.
- iii. During the download of the mymobility App to the iPhone, the coordinator and subject will:
 - Verify that the phone and Apple Watch operating systems (iOS and Watch OS) software are current.

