| all attempts to contact the subject are unsuccessful or the subject is contacted and chooses to withdraw from the study | A Study Completion Form will be completed and will specify the reason the subject is no longer participating in this study. If the subject has already received an Apple Watch, the coordinator will have the subject unpair and return the Apple Watch as soon as possible and will track this on the Device Accountability Log. Return mailers will be provided for subjects who have moved or are unable to come into the clinic to return the Apple Watch. Subjects will be instructed that they may uninstall the mymobility and/or Apple Health and Fitness Recorder Apps if desired. |

If attempts are made to contact a patient to schedule a visit and the patient is determined to be lost to follow-up, then additional attempts will not be required for watch retrieval.

7. Protocol Deviations

Investigators should not deviate from the study protocol unless it is to eliminate hazard to the patient. If a protocol deviation does occur, the deviation must be documented on the **Protocol Deviation Form** and submitted to the Sponsor. Each significant deviation will be reported to the IRB/EC, if applicable, within the appropriate deadlines stipulated by the appropriate regulatory authorities. Significant deviations are defined as those impacting or potentially impacting patient safety.

Site-facing forms that are partially or completely missed should be documented as protocol deviations. Protocol deviations will not be required for patient-facing surveys that are partially or completely missed. Partially or completely missed patient surveys for patients enrolled under a previous protocol version will also not require protocol deviations. Additionally, protocol deviations will not be required for out of window patient-facing surveys.

Chart reviews are required at the 3 month and 1 year intervals. The intention is that the review identifies potential medical and adverse events that have not been previously reported. A chart review will provide the same information whether it is completed in-window or late out-of-window. As such, protocol deviations will not be required for conducting late chart reviews.

8. Study Termination

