The RCT cohort will include 1,000 subjects. This is based on the sample size of 794 required to show non-inferiority on the readmission rate endpoint. Accounting conservatively for 20% Loss-to-follow-up, 1,000 subjects will ensure the study is adequately powered. This study is powered appropriately to show non-inferiority between the mymobility group and control group.

- i. This study is designed to show that the mymobility group is non-inferior to the control group using one primary study endpoint. This will be shown using a closed testing method in which the primary endpoint of readmission rate is compared using $\alpha=0.05$. Study success requires that the study group successfully demonstrates non-inferiority on this end point using the statistical methods described.

2. Apple Watch/mymobility Correlative Analytics

Although there is no well-defined method to calculate the power of a predictive model before it has been developed, the low rate of certain outcomes such as manipulation under anesthesia, readmission, embolism, etc. will increase the number of subjects needed to create a reliably predictive tool that could be used to correlate events and data in order to make claims in clinical decision making. Generally, very large numbers are required to demonstrate predictive power for a predictive statistical model. A goal of 10,000 subjects has been set, with interim analyses at 2,500, 5,000 and 7,500 subjects to determine continued need for subject enrollment. Assuming a complication rate of ~3% and a discharge rate of ~5% to postoperative rehab facility in the study population of 10,000 subjects in the Correlative Analytics Cohort, this implies that 300 subjects will have some type of complication and 500 subjects will be discharged to a rehab facility. Given the fact that our goals are to identify high positive predictive value and area under the curve (AUC) upper and lower threshold values of Apple Watch measured and transmitted biometric data (steps, stand hours, active calories, exercise minutes, heart rate - resting, walking, variability, flights climbed), using multivariate regression to correlate with post-op complications, and risks of discharge to rehab facility, we would conclude that a Predictive Signatures Study group of at least 10,000 subjects will be required.

Examples of other studies in the total joint literature that have used multivariate regression models to provide clinically useful cutoff values are provided below:

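### The plan does not require 30-day readmission status for RCT subjects who leave before the 3-month chart review, so the non-inferiority test may rest only on recorded cases

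*Combined protocol and SAP*

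**What the plan says.** **Sizing.** Section XVI.B states: "Based on an assumed readmission rate of 5.4% in both the control and study group", with "a non-inferiority margin of 4.5" percent, and "a total sample size of 794 patients will provide 80% power while controlling the alpha-error at 0.05". Section XVI.C.1 then adds: "Accounting conservatively for 20% Loss-to-follow-up, 1,000 subjects will ensure the study is adequately powered". The 20% is not split by arm and is not tied to day 30.

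**End of collection.** Section X.H says "data will continue to be collected until the subject completes the study per the protocol, voluntarily withdraws from the study", and goes on to list withdrawal by the investigator, loss to follow-up, revision that removes the implant, and death.

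**Chart review.** Section XII.D.7 says "Chart reviews are required at the 3 month and 1 year intervals". Section X.H lists readmissions among the items reviewed. Late review is accepted without a deviation. No section says whether the chart is reviewed after a subject has left.

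**Loss to follow-up.** Section XII.D.6 requires two consecutive missed visits and failed contact attempts. Section XII.D.8 also lets non-response to the 1-year surveys count as loss.

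**Analysis.** Section XVI.A describes descriptive summaries. Section XVI names no analysis set, missing-data method or sensitivity analysis for the primary test. The one explicit statement about who stays in the analysis, in Section XI.A.3, concerns mymobility subjects who receive physical therapy.

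**The concern.** The RCT has one confirmatory claim, non-inferiority on 30-day all-cause readmission, and in a non-inferiority test lost events can help the claim. If readmitted study-arm subjects are more likely than others to have no recorded status, leaving them out lowers the observed study-arm rate and pulls the difference towards zero.

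The plan has ways to learn the endpoint without an attended visit, but it does not require their use for subjects who have left, and the stopping rule in Section X.H reads the other way. The sample size allows for up to 20% without usable data, while the expected event rate is 5.4%. Even a modest link between leaving and readmission could therefore matter if missingness at day 30 came near that allowance.

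**Working it through.** **1. Reproduce the plan's figure.** Inputs from Section XVI.B: 5.4% in both arms, a margin of 4.5 percentage points (absolute scale inferred), 80% power, alpha 0.05 with sidedness not stated.

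n per arm = 2p(1−p)(z_alpha + z_power)² / margin²

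= 2 × 0.054 × 0.946 × (1.960 + 0.842)² / 0.045² = 396.002, rounded up to 397, or 794 in total.

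This matches with one-sided alpha 0.025. One-sided 0.05 would give 312 per arm, 624 in total. Allowing for 20% loss, 794 / 0.80 = 992.5, so 993, which the plan rounds to 1,000. The sample-size arithmetic is sound.

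**2. Error rate if only recorded cases are tested.** Put the truth at the margin: control 5.4%, study 5.4 + 4.5 = 9.9%. Let d be the share missing in each arm, and k the ratio of the probability of being missing for readmitted versus non-readmitted subjects. The documents give neither d at day 30 nor k; both are assumptions.

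- Probability missing if not readmitted: q = d / (k·p + 1 − p)
- Observed rate: p(1 − kq) / (1 − d)
- False non-inferiority: Φ((0.045 − observed difference)/SE − 1.96), unpooled SE, n = 500(1 − d) per arm

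Example with d = 20%, k = 2, informative in the study arm only:

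- q = 0.20 / (0.198 + 0.901) = 0.182, so 36.4% of readmitted subjects are missing.
- Observed study rate = 0.099 × 0.636 / 0.80 = 7.87%; difference from 5.4% = 2.47 points.
- SE with 400 per arm = 0.0176.
- Φ((0.045 − 0.0247)/0.0176 − 1.96) = Φ(−0.81) = 21.0%.

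| Missing per arm | Informative in | k = 1 | k = 1.5 | k = 2 | k = 3 |
|---|---|---|---|---|---|
| 5% | study arm only | 2.5% | 3.4% | 4.4% | 6.8% |
| 20% | both arms | 2.5% | 4.4% | 7.0% | 15.8% |
| 20% | study arm only | 2.5% | 8.5% | 21.0% | 61.6% |

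**3. Tipping point.** Suppose 400 subjects per arm have recorded status and both arms show 5.4%. The upper 95% bound is 1.96 × √(2 × 0.054 × 0.946 / 400) = 3.1 points, so the test passes. Now add 100 missing subjects per arm, with missing controls at 5.4% and missing study subjects at 13.1%:

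- Study rate = (400 × 0.054 + 100 × 0.131) / 500 = 6.94%; difference = 1.54 points.
- SE = √(0.054 × 0.946/500 + 0.0694 × 0.9306/500) = 0.0152.
- Upper bound = 1.54 + 1.96 × 1.52 = 4.52 points, which exceeds 4.5.

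Non-inferiority is lost at about 13.1% readmission among the missing study subjects.

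**4. Power with full ascertainment.** With no true difference, 400 per arm gives 80.4% and 500 per arm gives 88.3%.

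**The case against.** The strongest reply is that few subjects need lack the endpoint. Loss needs two consecutive missed visits, and the first two postoperative visits are at days 30 and 90. Loss after surgery is therefore normally declared only once the 30-day period has closed and the 3-month chart review is due. Some of the 20% may be subjects who fail to answer the 1-year surveys. The Medical Event Log and Adverse Event Form run from surgery, a final evaluation is attempted at withdrawal, late chart review is accepted, and OrthoVal may supply readmissions at selected US sites. A revision itself requires an Adverse Event Form. All of this stands, and it is why day-30 missingness is probably below 20%. It does not close the gap: none of these routes is required after exit, and a site's chart may not show an admission elsewhere.

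A reader might go further in three ways that the documents do not support.

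- *That the plan specifies a complete-case analysis.* It does not. Sizing on 794 of 1,000 is consistent with dropping lost subjects, but the text is silent.
- *That 20% will lack 30-day status.* The allowance is not tied to day 30.
- *That the watch rule shows bias in the sponsor's favour.* Section X.C makes subjects free to leave "but for the requirement to return the watch if they withdraw prior to completing the final follow-up visit". That rewards staying. Controls receive no watch, and subjects using their own have none to return. The rule shows that leaving differs by arm, not which way any bias runs.

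**Conclusion.** The concern holds as a gap in ascertainment and analysis, not as a demonstrated bias. As written, the plan can leave 30-day status unrecorded for subjects who leave before the 3-month review, and it does not say how the non-inferiority test treats them.

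The effect ranges from none, when missingness is unrelated to readmission, through a few points of excess error at 5% missing, to a serious failure when the full 20% is missing and strongly informative in the study arm only. That last case is an extreme: with a ratio of 3, half of all readmitted study-arm subjects would have no recorded status. All these figures rest on one-sided alpha 0.025, inferred from the reproduced sample size, and on assumed missingness ratios. This is a cheap improvement.

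**What to change.** In Sections X.H and XVI:

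1. Require day 0-30 readmission status, through the existing chart review form or OrthoVal where available, for every randomised and operated RCT subject. Include those who withdraw, are lost, or are terminated after revision, unless they revoke access to their records.
2. Analyse these subjects by allocated arm.
3. Report the number with unknown status in each arm, with a tipping-point analysis over the missing readmission rates beside the non-inferiority result.

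The cost is amended wording, some extra chart reviews at exit and one sensitivity analysis. No further subjects are needed, and fuller ascertainment raises power towards the 88.3% shown above. The limit is that Section X.C lets subjects withdraw authorization as well as consent. Those who do so stay unknown, which is why the third step is needed even if the first is well carried out.
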